12.2 Analysis Populations

- **The intent-to-treat (ITT) population** will include all patients randomized to a treatment group who complete the baseline evaluations. The ITT population will be used for the primary analyses of all study endpoints, taking into consideration the specific populations described below.
- **The per-protocol (PP) population** will include all patients randomized to a treatment group to whom at least 5 cycles of study treatment are administered in accordance with the protocol. The PP population will serve as the basis for secondary analyses of all study endpoints, taking into consideration the specific populations described below.
- **The FEV₁ population** will include all patients who have validated FEV₁ values (values judged to be obtained from adequate expiratory curves by central review) for at least 4 time points of the study comprising at the minimum the baseline and Day 161 assessments.

- **The PEx subset population** will include all patients who experience an IV antibiotic treated PEx episode during the study after completing at least one cycle of study drug treatment.
- **The safety population** will include all patients randomized to a treatment group who received at least one dose of study drug treatment. This population will serve as the basis for analyses of all safety endpoints.
- **The pharmacokinetic population** will include all patients randomized to the LAU-7b treatment group and provided the C_{\min} blood samples. This population will serve as the basis for the between-group comparison of the steady-state fenretinide pharmacokinetics grouped according to the *a priori* stratification factors and to compare the results with those obtained during the prior Phase Ib study.

12.3 Baseline and Demographic Characteristics

Demographic and baseline data will be summarized by treatment group using descriptive statistics. Demographics will include, among others, date of birth, gender, ethnicity, weight, height, body mass index. Childbearing status and pregnancy test results will be summarized descriptively for each treatment group. Protocol deviations/violations will be provided as a patient data listing only. Major protocol deviations/violations will be identified for analysis purposes.

The demographics and baseline characteristics summary will be presented for the ITT and the PP populations to allow review of the characteristics of those included in the efficacy analyses, which will be based on these analysis sets. The PEx subset will also be summarized separately.

12.3.1 Prior and Concomitant Medications

Medications used in this study will be coded by using the World Health Organization Drug Dictionary Enhanced and categorized as the following:

- **Prior medication:** Any medication that started before the first dose of study drug, independently of when it ended.
- **Concomitant medication:** Medication continued or newly received at or after first dose of study drug to the last follow-up (4 weeks after the last dose of study drug).
- **Post-treatment medication:** Medication continued or newly received after the last follow-up (4 weeks after the last dose of study drug).

A given medication can be classified using the above, in one or more categories. If a medication has a missing or partial missing start/end date or time and cannot be determined whether was taken before the first dose of study drug, concomitantly, or after 4 weeks after the last dose of study drug, it will be considered as prior, concomitant, and post-treatment. Prior medications and concomitant medications will be summarized descriptively based on the ITT population. Post-treatment medications will be listed for each patient.

12.3.2 Study Drug Exposure

The duration of study drug exposure is defined as follows: Last dose date minus first dose date plus 1 day, regardless of any interruptions in dosing. If the last dose date of study drug is missing, the patient's discontinuation or completion date will be used for analysis purpose. Duration of study drug exposure will be summarized descriptively as a continuous variable (number, mean, SD, median, minimum, and maximum), by study group, using the safety population subset of the ITT population.

12.3.3 Study Drug Compliance

Study drug compliance will be performed on the Safety population. Study drug compliance will be assessed by calculating as follows: $100 \times (1 - [\text{total number of days of study drug interruption}] / [(\text{duration of study drug exposure}) - (\text{total duration of planned drug free intervals})])$. The total number of days of study drug interruption is defined as the sum of (number of days of each study drug interruption), where number of days of each study drug interruption is defined as the interruption end date minus the corresponding interruption start date plus 1 day. Treatment compliance percentages will be summarized descriptively as continuous variables (number, mean, SD, median, minimum, and maximum). The percentage of patients whose compliance is $<80\%$ or $\geq 80\%$ will be summarized, by study group.

12.4 Efficacy Analysis

12.4.1 Analysis of Primary Endpoint

The study will be considered successful if a statistically significant advantage for fenretinide over placebo is obtained for the absolute change in FEV₁ percent predicted from baseline to Week 24.

Values for percent predicted FEV₁ as well as their change relative to baseline will be tabulated by time point and descriptive statistics will be used. In the analysis for the primary efficacy endpoint, change from baseline in FEV₁ % predicted (absolute change), including all measurements up to Week 28 (both during and after treatment measurements, including after treatment discontinuation) will be analyzed based on a mixed-effect repeated-measure model. Even though no imputations will be used in the primary analysis, a sensitivity analysis will be conducted where missing data points will be imputed using appropriate interpolation methods; extrapolation methods will be used for truncated FEV₁ % predicted values.

The planned model will include the absolute change from baseline in FEV₁ % predicted as the dependent variable; treatment, visit, and treatment-by-visit interaction as fixed effects; and patient as a random effect with adjustments for a) FEV₁ % predicted determined at the Screening/Baseline Visits (average where possible), b) PEx frequency in the prior year, and c) Co-administration or not of Kalydeco® (ivacaftor), Orkambi® (ivacaftor/lumacaftor), Symdeko® (ivacaftor/tezacaftor) or another commercially available CFTR modulator product. Additional post-hoc analyses may be performed in an exploratory manner depending on the frequency of other phenotypes or concomitant drugs. The primary result obtained from the model will be the treatment effect at Week 24. The estimated mean treatment effect, a 95% confidence interval, and a 2-sided P value will be generated. Alternative methods will be used if necessary due to data not meeting the standard requirements for the proposed analysis.

Full details will be specified in the SAP.

12.4.2 Analysis of Secondary Efficacy Endpoints

For all secondary efficacy endpoints, the primary analysis will be based on data obtained at Week 24 or cumulated up to Week 24.

Pre-defined Clinical Parameters:

- Count data variables: The time to first antibiotic use, the number of antibiotic treatments, the number of days of antibiotic treatment (other than chronic inhaled antibiotics already started prior to trial or oral chronic azithromycin) and the number of protocol-defined PEx will be tabulated by treatment and compared using Count regression will be used for the group comparison of the number of antibiotic treatments and the number of days of antibiotic treatment. The number of protocol-defined PEx will take

into account in the model of the time spent on study and considering the same covariates as those described below for the time to event data.

- Time to event data variables: The time to first protocol-defined PEx, the time interval between IV antibiotic-treated PEx episodes will be tabulated by treatment and compared using a Cox proportional hazards regression analysis. The model will include treatment as main effect with covariates for age category at baseline, FEV₁ % predicted category (as per entry stratification), PEx number category in prior year (as per entry stratification). A patient without exacerbation before withdrawal or completion of the study is considered censored at the time of withdrawal or completion of the study. If the proportional hazards assumption is violated, a stratified analysis will be conducted using stratified Cox regression. Additionally, Kaplan-Meier methods will be used to produce graphical presentations of the survival (exacerbation-free survival) by treatment and to estimate cumulative survival rates by treatment.
- Relative change (in %) in FEV₁ % predicted from baseline to Week 24: Analysis of this variable will be similar to that of the primary analysis of the primary efficacy endpoint
- Body weight and BMI changes from baseline/screening will be summarized using descriptive statistics by treatment and compared between treatments using a linear mixed-effects model with treatment as fixed effect; visit and treatment-by-visit interaction as random effects; and adjustment for FEV₁ % predicted category (as per entry stratification), PEx number category in prior year (as per entry stratification) and weight or BMI at baseline as covariates.

Pharmacodynamic Endpoints:

Values for AA, DHA and AA/DHA ratio as well as their change relative to baseline will be tabulated by time point and descriptive statistics will be used. The rate (frequency) of normalization (normalization meaning a parameter value reaching the mean parameter value observed in healthy controls ± 1 Standard Deviation) will be calculated for the end-of-treatment cycle values, and the treatments will be compared using two-sided multivariate logistic regression with baseline AA/DHA ratio as a covariate. Alternative methods will be used if necessary.

Values for pharmacodynamic parameters EPA, inflammation markers, metabolipidomic markers, systemic bone formation/resorption markers, markers of oxidative stress, ceramides), as measured in plasma (or serum, or blood, as required), as well as their change relative to baseline, will be tabulated by time point and descriptive statistics will be used. An analysis of variance will be used to compare treatments assuming datasets meet standard pre-requisites for such analysis (normal or log-normal distribution and homogeneity of variance). Alternative methods will be used if necessary.

Pharmacokinetic Endpoints:

Blood samples for fenretinide C_{min} analysis will be obtained from all patients randomized to fenretinide. Patients randomized to placebo will provide samples (to maintain the study blind) but will not contribute to the C_{min} dataset.

Plasma fenretinide C_{min} concentrations will be presented in a tabular summary, by sampling day and compared between groups of CF patients receiving fenretinide grouped according to the a-priori stratification factors.

Quality of Life Endpoints:

Quality-of-life data will be derived from the questionnaires according to the corresponding scoring manuals and will be summarized by treatment group. Patients' health state will be derived from the CFQ-R questionnaire, including the extracted CFQ-R respiratory domain, a separate endpoint. Additional exploratory health condition will be evaluated by the Matouk Disease Score. Data will be summarized by treatment group using descriptive statistics. Analysis of the absolute change from baseline for the CFQ-R (overall and respiratory domain) will be performed similarly to that of the primary efficacy endpoint with the addition of the CFQ-R respiratory domain score at baseline as a covariate.

12.4.3 Analysis of Exploratory Endpoints

- On the subset of patients that exacerbates and are treated with IV antibiotics, the changes of selective biomarkers in blood, serum and plasma from prior to the start of IV antibiotics to after the IV antibiotic treatment will be summarized by treatment group and analyzed using descriptive statistics. The mean changes will be compared between fenretinide and placebo using parametric and non-parametric statistics, where appropriate.
- The overall change in the *PsA* density in the sputum, from baseline through 12 and 24 weeks of treatment, and the AUC of the CFU from baseline to 24 weeks will be the variables studied for this investigation. Data will be summarized by treatment group and analyzed using descriptive statistics. The mean changes and the AUC data will be compared between fenretinide and placebo using parametric statistics assuming datasets meet standard pre-requisites for such analysis (normal or log-normal distribution and homogeneity of variance).
- The overall change in lumbar spine bone mineral density, from baseline to last follow-up on Week 28 will be summarized by treatment group and analyzed using descriptive statistics. The mean changes will be compared between fenretinide and placebo using parametric statistics assuming datasets meet standard pre-requisites for such analysis (normal or log-normal distribution and homogeneity of variance).
- Data from this trial may be collected and analyzed in various other retrospective analyses as detailed in the SAP.

12.5 Safety Analyses

The safety analyses will be performed at least thrice, 1- when a minimum of half of the enrolled patients have completed at least one dosing cycle and corresponding safety information is available, along with Day 21 plasma retinol and retinol binding protein concentration data, 2- when at least half of the enrolled patients have completed a minimum of 3 dosing cycles and corresponding safety information is available, along with Day 77 plasma retinol and retinol binding protein concentration data, and 3- at the time of final analysis. Safety analyses will be performed on the safety population (those patients who receive at least one dose of study drug). Blinded safety data will be assessed by the DSMB at regular meetings. The DSMB may request unblinding of patients for safety concerns in addition to receiving the unblinded mid-study analysis results. The study will remain double blinded to the Investigators, patients and sponsor's staff until the end of the study, unless circumstances require unblinding.

Safety and tolerability will be assessed by the following:

- Adverse events described and categorized according to the MedDRA, version 16 or more recent.
- Clinically relevant changes from baseline in vital signs
- Clinically relevant changes from baseline in 12-lead ECG
- Clinically relevant changes from baseline in physical examinations
- Clinically relevant changes from baseline in safety laboratory assessments (hematology with differential count, biochemistry, and urinalysis)

- Plasma retinol and retinol-binding protein values, changes from screening/baseline, correlated with ophthalmological symptoms, more specifically nyctalopia
- Change in PEx incidence and antibiotic treatment requirement.

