7.2.2 DSMB Review

Throughout the study, the DSMB will monitor blinded safety measures and demographics at regular intervals as specified in the DSMB charter, or as requested by the DSMB chair. The DSMB will receive reports of adverse events by organ class, with emphasis on SAE’s, clinically significant adverse events with a high causality potential to the study treatment, PEx episodes, and adverse events in the ophthalmological and dermatological class. Members of the DSMB will not be directly involved in the conduct of the study and cannot serve as Investigators in this study.

The DSMB will be composed of:

- Two physicians involved in the care of CF patients, experienced in clinical research, independent of Laurent Pharmaceuticals and not involved as an Investigator on the study.
- One Ophthalmologist experienced in clinical research, independent of Laurent Pharmaceuticals.
- One study biostatistician that can be unblinded with regards to patient randomization, meaning that it is not involved in the statistical design, analysis and reporting of the study.
- Ad-Hoc members recruited to provide specific expertise and meet the Board's mandate.

Each DSMB member will sign a Conflict of Interest Statement which includes current affiliations, if any, with pharmaceutical and biotechnology companies (e.g., stockholder, consultant), and any other relationship that could be perceived as a conflict of interest related to the study and / or associated with commercial interests pertinent to study objectives.

Data will be presented in a blinded manner during the open sessions of the DSMB unless noted otherwise below. At DSMB meetings data and discussion are confidential. Participant identities will not be known to the DSMB members.

Mandate of the DSMB (to be defined in greater detail in the DSMB Charter):

- Review safety information emerging from the study (and any other study of fenretinide). Particular attention will be paid to PEx incidence and due to the profile of fenretinide, ocular and dermatological AEs. Moreover, the DSMB will have access to the randomization code, if justified.
- Meet at specific times of the study to review the safety data cumulated to date. The following specific times have been selected a priori:

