 - When a minimum of half of the enrolled patients have completed at least one dosing cycle and corresponding safety information is available, along with Day 21 plasma retinol and retinol binding protein concentration data. This will not be a full unblinding; it will be an unblinded safety analysis of Active versus Placebo;
 - When a minimum of half of the enrolled patients have completed the first 3 dosing cycles and corresponding safety data is available for review. This will not be a full unblinding; it will be an unblinded safety analysis of Active versus Placebo;
 - Outside of the above, every 6 months;
 - Anytime as needed for review of clinically significant safety information brought to the attention of the DSMB.
- Provide guidance to the study team with regards to safety trends. Recommendation to implement a systematic dose reduction or continue the study at the planned dose level will be made by the DSMB and reviewed by the Laurent Pharmaceutical's Team, who will take the final decision to pursue dosing or not (see Sections 7.2.3, 7.2.4 and 8.4.1 for Study/Treatment Arm Stopping Rule Guideline, Treatment Arm Dose Reduction Guideline, and Individual Patient Stopping Rules, respectively).

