7.2.3 Study / Treatment Arm Stopping Rule Guideline

The following should serve as a guide for the DSMB to recommend stopping the enrolment and/or further drug administration in a given treatment arm. An agreement will be reached with the DSMB on the guideline prior to the study. Other considerations may be used to arrive at such decisions, which must involve Laurent Pharmaceuticals Executive Management.

- Occurrence of any case of death that may be attributed to fenretinide (in such a case, the blind will have to be broken and allocated treatment identified);
- Occurrence of an increased number, relative to placebo, of unexpected SAEs that could be attributable to the drug (at least *probable* causality relationship) that raise Investigators/DSMB concerns about patients' safety;
- Increased frequency and/or severity of drug-related adverse events, relative to placebo, that in the judgment of the Investigators/DSMB, will result in the advice to discontinue fenretinide treatment.

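### Two of three stopping guidelines compare with placebo, yet after half of patients finish cycle 3 the DSMB gets by-arm safety tables before the final analysis only if it asks

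*Protocol*

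**What the plan says.** **Stopping guidelines.** Protocol 7.2.3 gives the DSMB three guides. The one on deaths needs no comparison. The other two do: "Occurrence of an increased number, relative to placebo, of unexpected SAEs" (at least probably attributable to drug), and "Increased frequency and/or severity of drug-related adverse events, relative to placebo".

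**By-arm looks.** Protocol 7.2.2 and SAP 3.19 schedule two, at half of enrolled patients through one cycle and at half through three. Each is described in the same way: "This will not be a full unblinding; it will be an unblinded safety analysis of Active versus Placebo". Other meetings are six-monthly or as needed, with no by-arm wording.

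**Default format.** In 7.2.2, "the DSMB will monitor blinded safety measures and demographics at regular intervals", and "Data will be presented in a blinded manner during the open sessions of the DSMB unless noted otherwise below". Section 12.5 says the same of regular meetings: "Blinded safety data will be assessed by the DSMB at regular meetings". It plans at least three safety analyses: the two looks and the final one.

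**Other routes to by-arm data.** Section 7.2.2 provides "One study biostatistician that can be unblinded with regards to patient randomization" among the members and adds that "the DSMB will have access to the randomization code, if justified". Section 12.5 lets the DSMB ask for patients to be unblinded over safety concerns. Section 7.3.2 sends SAEs to the DSMB chair, who can do the same.

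**The concern.** A guideline that compares arms needs data by arm. After the second look none are scheduled until the final analysis.

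The gap falls on the exposure that is newest in cystic fibrosis. Phase Ib (5.4.4.1, 5.4.5.1) gave three 21-day cycles at rising doses, only one of them at 300 mg. Its drug-free gaps averaged 57 and 27 days (5.4.5.2), against 7 days here. Section 7.1.2 gives longer treatment as a reason for making safety co-primary.

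Scheduled checks are also sparser late in treatment. After Day 77 the night vision questionnaire is next given on Day 161, and the next planned eye examination is on Day 189. No clinic visit is planned between Days 105 and 161. Section 12.5 ties retinol data to the Day 21 and Day 77 looks only.

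At stake is how early the DSMB would notice that, for example, moderate eye, skin or respiratory events are more frequent or more severe on LAU-7b. Exacerbations and other disease-related events are expected in both arms, so a pooled table can hide such a difference.

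**Working it through.** **Step 1: count from the text.** Comparative guidelines in 7.2.3: 2 of 3. Scheduled by-arm DSMB reports: 2. Scheduled by-arm reports between the second look and the final analysis: 0. Protocol and SAP agree.

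**Step 2: guaranteed exposure at look 2.** The plan gives no exposure figure to reproduce. With 136 patients and 6 cycles each, the trigger guarantees only 68 × 3 / (136 × 6) = 25% of planned patient-cycles.

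**Step 3: likely exposure at look 2.** Inputs from the documents: 136 patients; 21 days on and 7 off; six cycles. Cycles 4-6 therefore hold 136 × 63 = 8,568 dosing days. Assumptions, because the documents are silent: uniform accrual over 3 to 24 months with mid-interval entry times, no dropout, months of 30.44 days, half meaning 68 patients, and data cumulated to the date of review. Look 2 is set at the 68th patient's Day 77 plus a reporting lag.

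Example, 12 months' accrual and no lag:
- 68th entry: 67.5/136 × 365.3 = day 181.3. Look 2: 181.3 + 77 = day 258.3.
- Last Day 161 visit: 135.5/136 × 365.3 + 161 = day 524.9.
- Interval: 266.6 / 30.44 = 8.8 months.
- Summing each patient's cycle 4-6 dosing up to day 258.3 gives about 37% of 8,568 days.

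| Accrual (months) | Cycle 4-6 days covered, no lag | 30-day lag | 60-day lag | Months from look 2 (no lag) to last Day 161 |
|---|---|---|---|---|
| 3 | 11% | 33% | 65% | 4.3 |
| 6 | 25% | 41% | 58% | 5.8 |
| 12 | 37% | 45% | 54% | 8.8 |
| 18 | 41% | 47% | 52% | 11.8 |
| 24 | 43% | 48% | 52% | 14.8 |

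Not covered: 57-89% with no lag, 52-67% with 30 days, 35-48% with 60 days. Over all dosing days, look 2 covers 47-49% with no lag.

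**Step 4: what added reports would cover** (no lag).
- Six-monthly by-arm reports timed from look 2 and before the last Day 161 visit: none at 3 or 6 months' accrual, one at 12 or 18, two at 24. On a fixed calendar from first dose the counts are 1, 1, 1, 2 and 2, so this depends on the convention.
- A report when 68 patients reach Day 161 exists in every scenario, 1.5 to 12 months before the last Day 161 visit.
- With both, timing the six-monthly reports from look 2, the latest report before that visit covers 70-93% of cycle 4-6 dosing days.

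**The case against.** The strongest reply is that the DSMB is well supplied and not shut out. Clinically significant eye findings are forwarded to it (11.5), and these are the drug's best-documented toxicity. Its reports stress high-causality, exacerbation, eye and skin events (7.2.2). It assesses AEs reported by sites (11.1.1), may ask for unblinding over any safety concern (12.5), and may meet at any time. The 7.2.3 list is only a guide, and the dose-reduction guideline in 7.2.4 has no placebo comparison. Long-term non-CF data exist (5.4.4.2). For a 136-patient Phase II trial, blinded review with two by-arm looks is a coherent model. The charter and DSMB mock tables may already provide closed-session reports: mention of open sessions suggests closed ones, and 12.5 sets a minimum of three analyses, not a maximum.

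Most of this stands. A reader might infer that the stopping guidelines cannot be applied after look 2, or that drug-related AEs have no case-by-case route to the DSMB. The documents support neither reading.

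What does not go away is that a request needs a trigger. Case referral shows individual events, and pooled tables show totals. Neither shows a difference in rates between arms. Section 12.5 also states a blinded format for regular meetings, so the visible text is not simply silent.

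The objection to the size also stands in part. The trigger requires data to be available, so zero lag is an extreme. Reading half as half of those enrolled to date, or an earlier data cut, would move look 2 the other way. The documents do not settle which applies.

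**Conclusion.** The point holds in a limited form. After the second look, a by-arm comparison of AE frequency or severity reaches the DSMB before the final analysis only on request, although two of three stopping guidelines rest on such a comparison. The exposed case is an imbalance in non-serious events. Single serious or ocular events are covered.

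Roughly 35-89% of cycle 4-6 dosing falls after the last scheduled by-arm look. The range rests on the assumed accrual, lag and absence of dropout. It would be tempting to cite the 89% alone, but that needs both 3-month accrual and no reporting lag.

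This is a worthwhile, inexpensive improvement, not a defect that invalidates the monitoring plan. Confidence is moderate because the charter could not be read.

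**What to change.** Amend Protocol 7.2.2 and 12.5 and SAP 3.19, and align the charter, along these lines: at each 6-monthly meeting, and when half of the enrolled patients have completed cycle 6, the DSMB biostatistician who can be unblinded presents the active-versus-placebo safety tables in closed session. Sponsor, sites and open sessions stay blinded. The cycle 6 trigger is included because six-monthly meetings alone may add nothing if accrual is fast. Section 7.2.3 needs no change. If the charter already provides this, correct the blinded-data wording in 7.2.2 and 12.5 and state the schedule in SAP 3.19.

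Cost: wording changes, one added report and reruns of existing tables, with no new data or staff. The downside is slightly wider DSMB access to by-arm results, including exacerbations, which are also a secondary efficacy endpoint. The plan has no efficacy stopping rule, so no alpha is spent and the sample size is unaffected.
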